## 2. STUDY DOCUMENTS

The following study documents are used for the preparation of the statistical analysis plan (SAP):

- Protocol version 3.0, dated 08 January 2019
- Annotated electronic case report form (eCRF) version 1.0, 11 September 2018
- Data management plan version 1.0, 23 August 2018

## 3. STUDY OBJECTIVES

### 3.1 Primary Objective

To demonstrate that dasiglucagon is superior to placebo following a single injection of 0.6 mg of dasiglucagon in treating hypoglycemia in children with type I diabetes mellitus (T1DM)

### 3.2 Secondary Objective

- To confirm that a single dose of dasiglucagon [0.6 mg] is comparable to a single dose of GlucaGen® [1 mg/mL] in treating hypoglycemia in children with T1DM (in accordance with the label, children below 25 kg body weight will be administered 0.5 mg GlucaGen®)
- To assess safety profile of dasiglucagon in children with T1DM
- To assess pharmacokinetic (PK) profile of dasiglucagon in children with T1DM

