10.1.3.2 Primary efficacy endpoint

The primary endpoint, time to plasma glucose recovery, will be summarized using Kaplan-Meier estimates for each treatment group in total and stratified by age group and injection site. The median time to recovery with 95% confidence interval will be estimated by treatment group, in total and in each stratum.

A stratified log-rank test will be applied to compare the dasiglucagon 0.6 mg treatment group to the placebo group. The same method will be applied to compare dasiglucagon 0.6 mg with GlucaGen®.

In the primary analysis, recovery cannot be achieved in those patients where IV glucose treatment is administered. Those patients who receive IV glucose will be censored (i.e. set to 'not recovered') at 45 minutes after dosing.

A further sensitivity analysis will be done by censoring data at the actual time when the patients received glucose IV.

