10.1.3.3 Secondary efficacy endpoints

The secondary efficacy endpoints are plasma glucose recovery within 10, 15, 20 and 30 minutes after trial product injection, i.e. achieving a ≥ 20 mg/dL increase in plasma glucose from baseline within 0 to 10, 15, 20 and 30 minutes. If a patient has received an IV glucose treatment before recovery, the patient is set to 'not recovered' in the analysis of the 4 endpoints, corresponding to censoring in the time-to-recovery analysis for the primary endpoint. The 10-, 15-, 20- and 30-minute recovery rates of 2 treatment groups will be compared by a Cochran-Mantel-Haenszel test stratified by age group and injection site. The treatment and age group responder rates with the 95% confidence intervals will be presented for the 10-, 15-, 20- and 30-minute endpoint.

If due to small or zero cell counts the Cochran-Mantel-Haenszel test fails, non-stratified Fisher's exact tests will be applied instead.

Plasma glucose changes from baseline at 10, 15, 20 and 30 minutes after trial product injection will be analyzed in an analysis of variance with factors treatment (3 levels) age group (2 levels) and injection site (2 levels) for each endpoint. If the rescue IV glucose was administered before 10, 15, 20 or 30 minutes, respectively, the patient's plasma glucose changes from baseline will be determined from the value at the time of rescue IV glucose administration. Adjusted treatment means will be presented with their 95% confidence intervals. The 4 analysis of variance will also be used to test the difference between treatments adjusted for age group and injection site.

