## 10.7 Multiple Comparison/Multiplicity

For the confirmatory analyses of the primary and secondary endpoints, patients treated with either dasiglucagon 0.6 mg and or placebo will be compared. A hierarchical procedure will be applied for the control of multiplicity. The primary and secondary endpoints will be evaluated on the FAS.

For the confirmatory analyses, the following a priori-defined hierarchical inferential test order will be applied for the control of the type 1 error rate across the planned multiple comparisons. The primary endpoint and secondary endpoints will be inferentially evaluated within the FAS in the following order, where inference will proceed at the 2-sided 0.05 criterion significance level until the first failure to reject the null hypothesis for a dasiglucagon versus placebo comparison:

- Primary: Time to plasma glucose recovery
- Secondary 1-4: Plasma glucose recovery within 30 minutes, within 20 minutes, within 15 minutes, and within 10 minutes after study drug injection without administration of rescue IV glucose.
- Secondary 5-8: Plasma glucose changes from baseline at 30 minutes, at 20 minutes, at 15 minutes, and at 10 minutes after study drug injection or at the time of rescue.

The GlucaGen® versus placebo comparisons will not be included in the inferential testing hierarchy, since the efficacy of GlucaGen® is previously established, and these comparisons are intended to support the validity of the study for the dasiglucagon versus placebo comparisons. Moreover, the comparison of dasiglucagon versus GlucaGen® is not part of this hierarchical testing procedure.

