## 11. METHODS OF EFFICACY ANALYSIS

### 11.1 Primary Efficacy Analyses

The primary endpoint, time to plasma glucose recovery, will be summarized using Kaplan-Meier estimates per treatment group.

The actual time points at 0, 4, 6, 8, 10, 12, 15, 17, 20, 30, 45 and 60 minutes will be used in the analyses.

Kaplan-Meier plots will be created showing the the estimated survival function for each treatment in one plot.

In the primary analysis, recovery cannot be achieved in those subjects where rescue IV glucose treatment is administered. Those subjects who receive rescue IV glucose will be censored (and set to 'not recovered') at 45 minutes after dosing.

For patients who did not recover within 45 minutes after dosing, time to recovery is censored at 45 minutes.

The stratified log-rank test will be applied to compare the dasiglucagon 0.6 mg treatment group to the placebo group. The same method will be applied to compare dasiglucagon 0.6 mg with GlucaGen®, but not considered for the confirmatory hierarchical testing procedure.

In order to facilitate this, SAS procedure proc lifetest is used. The following code will be used, but minor variations can be applied during programming:

```
proc lifetest data=xx plots=survival(atrisk=0 10 15 20 30 45);  
  time aval * Status(0);  
  strata age site/ group= treat test=logrank diff=all;  
run;
```

where "aval" is the time to plasma recovery, and "status" is a censor variable for patients who receive IV glucose. Age group and injection site are the stratification variables and "treat" the planned treatment assignment.

The unstratified result of the log-rank test can be obtained from the following code:

```
proc lifetest data=xx plots=survival(atrisk=0 10 15 20 30 45);  
  time aval * Status(0);  
  strata treat / test=logrank diff=all;  
run;
```

In sensitivity analyses, the time to plasma glucose recovery will be analyzed

- 1) without censoring for those subjects who require rescue IV glucose before 45 minutes and
- 2) with censoring at the time of administration of rescue IV glucose before 45 minutes.

As a supportive analysis to the stratified log-rank test for the time to plasma glucose recovery, dasiglucagon will be compared to placebo using a Wilcoxon test stratified by age group and injection site.

To graphically describe recovery in time, a histogram showing the proportion of patients that recovered at each time interval will be created, one for each treatment group.

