The primary endpoint will additionally be analyzed using a discrete-time Cox proportional hazards (CPH) time to event statistical model, if the hazards by treatment group can be assumed

proportional using a graphical comparison of log-minus-log survival curves and no more than two-thirds of the recovery times are censored in each treatment group. The CPH model will be used for descriptive purposes, with treatment group, age group and injection site modeled as categorical effects, and baseline plasma glucose modelled as a continuous covariate. The treatment group hazard ratios of active versus placebo, will be estimated together with the 95% confidence intervals, and pairwise treatment group inferences (dasiglucagon vs placebo, GlucaGen vs placebo, dasiglucagon vs GlucaGen) will be evaluated using least-square mean and standard deviation estimates.

Due to the discrete nature of blood sampling in time, and the fact that there must be a true, but unmeasured, ordering of the recovery times, the method using the “exact discrete” partial likelihood for tied failure times will be applied. In SAS, this is implemented in the `phreg` procedure with the option `ties=discrete`. The influence of age and injection site on time to recovery will also be evaluated in the proportional hazards model by a ‘type 3’ test in the `phreg` procedure.

In addition, separate CPH models will be calculated to evaluate homogeneity for the following factors:

Sex, BMI class, ethnicity, race, US/non-US.

These additional homogeneity models are only presented for the primary efficacy analysis, but not for subsequent variants of that analysis.

To obtain an estimate of these true, but unassessed, patient recovery times, a linear interpolation (between the two time points before and after recovery is observed) will be carried out to estimate the patients’ actual time of recovery. These derived recovery times will be described and analysed in the same manner as for the discrete times above.

Let  $t_1$  and  $t_2$  be the 2 time points before and after recovery is observed and  $y_1$  and  $y_2$  be the corresponding changes from baseline in glucose concentrations, where  $y_1$  is below 20 mg/dL and  $y_2$  is greater than 20 mg/dL.

The interpolated time point  $t_{ext}$  is calculated then as:

$$t_{ext} = t_1 + \frac{(20 - y_1) * (t_2 - t_1)}{(y_2 - y_1)}$$

This linear interpolation is only used as a supportive analysis to the primary analysis model using `proc lifetest`.

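### The plan sets out to confirm that dasiglucagon is comparable to GlucaGen without a margin or decision rule, and does not clearly specify a dasiglucagon-GlucaGen estimate with a confidence interval

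*SAP*

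**What the plan says.** The objective in SAP 3.2, repeated in protocol section 6, is "To confirm that a single dose of dasiglucagon [0.6 mg] is comparable to a single dose of GlucaGen". It is listed first of three secondary objectives, although the documents do not rank them.

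The comparison is then handled as follows.

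- **Log-rank test.** After the placebo comparison, protocol 10.1.3.2 adds: "The same method will be applied to compare dasiglucagon 0.6 mg with GlucaGen". SAP 11.1 repeats this, "but not considered for the confirmatory hierarchical testing procedure", and SAP 10.7 says that "the comparison of dasiglucagon versus GlucaGen® is not part of this hierarchical testing procedure". The shell for Table 14.2.1.1 also lists a non-stratified log-rank p-value for this pair.
- **Cox model.** SAP 11.1 calls it descriptive. "The treatment group hazard ratios of active versus placebo, will be estimated together with the 95% confidence intervals", whereas the pairwise inferences (the last pair being "dasiglucagon vs GlucaGen) will be evaluated using least-square mean and standard deviation estimates") have no interval attached. One of two conditions for fitting the model is that "no more than two-thirds of the recovery times are censored in each treatment group".
- **Recovery rates.** SAP 11.2 names only dasiglucagon and placebo for the Cochran-Mantel-Haenszel test.
- **Change from baseline.** Protocol 10.1.3.3 says the analysis of variance will be "used to test the difference between treatments adjusted for age group and injection site", without naming a pair. SAP 11.2 narrows the test to dasiglucagon and placebo. It also promises a 95% CI for a treatment difference, again without naming the pair.
- **Shells (SAP Appendix D).** Table 14.2.1.1 gives this pair p-values only and sets the placebo hazard ratio to 1. The recovery-rate and change-from-baseline shells have a comparison column for dasiglucagon versus placebo only.
- **Sample size.** SAP 5 expects 10 GlucaGen patients to be enough for the comparison and shows no calculation.

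**The concern.** To confirm comparability, a plan needs either a margin with a rule or, at the least, an estimate whose interval shows which differences the data exclude. Here the objective uses a confirmatory verb, while every named inference on time to recovery has no difference as its null hypothesis. Failing to reject that null with 20 versus 10 patients says little about how far apart the two products could be.

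A report that followed the shells exactly would answer this objective with p-values and three sets of single-arm summaries. The risk is that a non-significant p-value against GlucaGen is then reported as confirmation. The one model that could give a between-active ratio may also drop out because of what happens in the placebo arm, which has no bearing on this pair.

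**Working it through.** **1. The plan's own power figure.** Inputs from SAP 5: exponential times, medians 10 and 50 minutes, 20 versus 10 patients, 45 minutes of follow-up, two-sided 5%.

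- Rates: ln 2/10 = 0.0693 and ln 2/50 = 0.0139 per minute.
- Recovery by 45 minutes: 1 − 0.5^(45/10) = 0.956 and 1 − 0.5^(45/50) = 0.464.
- Lachin's comparison of exponential rates, unpooled variance rate²/P(recovery): SE = √(0.0693²/(0.956×20) + 0.0139²/(0.464×10)) = 0.0171.
- z = (0.0693 − 0.0139)/0.0171 = 3.24, and Φ(3.24 − 1.96) = 0.900.

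The stated 90% reproduces. Other methods differ (for example 96% by Schoenfeld's formula and 88% by simulation of the stratified log-rank test), but this figure is not in dispute. It concerns placebo only; the documents give no corresponding figure for GlucaGen.

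**2. Precision against GlucaGen, continuous times.** The GlucaGen median is an assumption: 10 minutes, equal to dasiglucagon.

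- Expected recoveries: 20 × 0.956 = 19.12 and 10 × 0.956 = 9.56.
- SE of the log hazard ratio: √(1/19.12 + 1/9.56) = 0.396.
- 95% CI around a ratio of 1: exp(±1.96 × 0.396) = 0.46 to 2.17.

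**3. The same under `ties=discrete`.** SAP 11.1 specifies the exact discrete likelihood, under which the ratio is an odds ratio per sampling interval. Times were simulated with the same assumptions on the sampling grid 4, 6, 8, 10, 12, 15, 17, 20, 30 and 45 minutes, censored at 45, with a two-arm fit, no covariates and 3,000 runs. The median SE was 0.470, so the interval is exp(±1.96 × 0.470) = 0.40 to 2.5. The SAP's model has a third arm and covariates, so this is an approximation to it.

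**4. The other two endpoints.**

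- Recovery-rate difference (dasiglucagon minus GlucaGen), Newcombe interval, at an illustrative 18/20 versus 9/10: −22 to +31 percentage points.
- Difference in least-squares means, with 40 patients, three treatments, age group and site: half-width t(0.975; 35 df) × √(1/20 + 1/10) = 2.03 × 0.387 = 0.79 residual SD, assuming balance. The documents give no SD, so this cannot be put in mg/dL.

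**5. Loss of the Cox contrast.** The condition is read as applying to every arm. Two-thirds of 10 is 6.67, so 7 censored placebo patients are enough to drop the model.

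| Placebo median | Censored share 0.5^(45/median) | P(7 or more of 10 censored) |
|---|---|---|
| 50 min (SAP 5) | 0.536 | 0.237 |
| 100 min (assumed) | 0.732 | 0.733 |

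SAP 5 takes the placebo median to be above 50 minutes, so 24% is the favourable end. The condition on proportional hazards comes on top and is not quantified here.

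**The case against.** The strongest reply is that the plan already treats this comparison as non-confirmatory. SAP 5 includes GlucaGen as a reference, SAP 10.7 and 11.1 keep the pair out of the hierarchy, and the Cox model is labelled descriptive. That is right, and it protects the type I error of the placebo comparisons. It does not tell a reader what would count as comparable, and it leaves the objective's verb at odds with the analysis.

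A reader might infer that no dasiglucagon-GlucaGen interval is planned at all. The documents do not support that. SAP 11.2 fits three treatment levels and leaves open which treatment difference receives a CI, and SAP 11.1 names this pair for least-squares-mean inference. SAP Appendices A and C also allow layouts to change during programming, so a shell does not override the text. The ratio itself follows from Table 14.2.1.1 by dividing the two hazard ratios against placebo. Its interval does not, because those estimates share the placebo arm and their covariance is not shown. Medians, recovery rates and least-squares means with 95% CIs are planned for each arm, including GlucaGen. The accurate charge is therefore ambiguity in the text and omission from the shells.

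A reader might also infer that rescue glucose makes loss of the Cox model much likelier than step 5 shows. Protocol 7.4.5.2.2 requires at least 54 mg/dL at dosing, so a recovered patient has reached at least 74. The glucose trigger before 45 minutes in protocol 7.4.5.2.3 is below 54. Rescue should therefore fall mainly on patients who would be censored anyway. The symptom trigger could add some, but the documents give no rate, so no adjusted figure is offered.

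**Conclusion.** The point holds as an inconsistency between objective and analysis. As written, the plan cannot support a conclusion that dasiglucagon has been confirmed comparable to GlucaGen, and it does not clearly secure the interval that would let readers judge for themselves. If the two products were truly equal, the interval would still be compatible with roughly a twofold difference in recovery rate either way, and somewhat more on the discrete scale. That rests on exponential times, a 10-minute dasiglucagon median from SAP 5 and an assumed equal GlucaGen median. The 73% for loss of the Cox model rests on an assumed 100-minute placebo median; the 24% uses the planning value.

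It would be a mistake to read this as a threat to the trial's main result. The dasiglucagon-placebo test, its power and the hierarchy do not depend on this pair. Nor do the documents present the GlucaGen arm as a sized non-inferiority comparison that fell short. The matter should be fixed, but its consequence is confined to one secondary objective.

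**What to change.** - **SAP 3.2 and SAP 15.** State that the dasiglucagon-GlucaGen comparison is descriptive estimation and that a non-significant p-value is not evidence of comparability. List this among the changes to the protocol. Amend the protocol objective only if that is still feasible; the synopsis plans the last visit for the second quarter of 2019 and the SAP is dated 16 August 2019.
- **Table 14.2.1.1.** Add a dasiglucagon/GlucaGen ratio with a 95% CI that does not depend on the placebo censoring condition, for example from a fit of the two active arms, and name the ties option.
- **Table 14.2.2.1.** Add the difference in recovery rates with a 95% CI.
- **Change-from-baseline table** (14.2.2.3 in Appendix C; its shell carries the number 14.2.2.2). Add the least-squares-mean difference with a 95% CI, and name the pair in SAP 11.2.
- **SAP 5.** Replace the statement that 10 patients are enough with one saying that the GlucaGen arm supports descriptive estimation only. Give the expected precision under the SAP's own exponential assumption: about 0.46 to 2.17 for continuous times and about 0.40 to 2.5 under `ties=discrete`, with an equal 10-minute GlucaGen median stated as an assumption.

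SAP 6 treats anything added after unblinding as post hoc, so these changes need to precede it. They require no extra patients or data. The cost is SAP wording, a few table rows and a weaker claim against the marketed product.

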## 4. STUDY DESIGN AND PLAN

This is a phase 3, randomized, double-blind, placebo- and active-controlled, parallel-arm trial designed to assess efficacy, safety and PK of dasiglucagon versus placebo and versus GlucaGen® in children with T1DM. At the time of protocol finalisation it was anticipated that it will be conducted at 2-3 centers in Europe and 1-2 centers in the USA.

[figure not shown]
The trial will include the following periods (as illustrated in Figure 4-1).

- A screening period from Day -30 to Day -3

- A treatment period, from Day 0 to Day 1 (day of randomization and single dosing with trial product). Unblinded trial personnel will do the handling, preparation and administration of trial product. All trial assessments will be done by blinded trial personnel
- A follow-up visit at Day 28 (the end-of-trial visit)

**Figure 4-1 Overview of the Trial Design**

Abbreviation: PK=pharmacokinetic

The schedule of assessments (refer to the study protocol) gives an overview of the trial procedures. Patients should attend all visits on the designated day or as close to it as possible.

## 5. DETERMINATION OF SAMPLE SIZE

The primary comparison is between the dasiglucagon and placebo treatment arms. From phase 2 results, the median time to an increase of 20 mg/dL of the 0.6 mg dose was approximately 10 minutes. For placebo-treated patients, the median time to recovery is assumed to be more than 50 minutes. Assuming an exponential time-to-recovery distribution with median times of 10 and 50 minutes, a 2-sided log-rank test will be able to detect a difference between dasiglucagon 0.6 mg

and placebo with 90% power with a follow-up time of 45 minutes at a 5% significance level with 20 patients randomized to the dasiglucagon arm and 10 patients to placebo.

GlucaGen® is included as a reference to compare the responses and AE profile to dasiglucagon with those to a marketed product. It is expected that 10 patients in the GlucaGen® group will suffice for the comparison.

## 6. GENERAL ANALYSIS CONSIDERATIONS

The statistical analyses will be reported using summary tables, listings, and figures (TLFs). The International Council for Harmonisation (ICH) numbering convention will be used for all TLFs. Unless otherwise noted, all statistical testing will be 2-sided and will be performed at the 0.05 significance level. Tests will be declared statistically significant if the calculated  $P$  value is  $\leq 0.05$ .

All data obtained in this trial and documented in the eCRFs will be listed and summarized with statistics or frequency tables as appropriate. In case of termination of the trial, all data collected up to that time point will be included into the analysis.

Continuous variables will be summarized with means, standard deviations, medians, minimums, and maximums and valid cases. Other summaries (eg, quartiles, 5%, 95% intervals) may be used as appropriate. For PK parameters except Tmax, geometric mean and geometric % CV will be calculated.

Categorical variables will be summarized by counts and by percentage of patients in corresponding categories. Percentages for missing values are omitted and do not account for the percent calculation of other categories. Percentages are routinely based on the total category count excluding the missing category if not otherwise mentioned. Percentages showing a rate relative to the total number of patients in this group are given in special tables (eg, adverse event [AE] tables). Footnotes will specify the percent basis in those cases.

All summary tables will be presented by treatment group if possible and also include a total summary column.

Individual patient data obtained from the eCRFs, external vendors, and any derived data will be presented by patient in data listings.

The analyses described in this plan are considered a priori, in that they have been defined prior to breaking the blind.

Any analyses performed subsequent to breaking the blind will be considered post hoc and exploratory. Post hoc analyses will be labeled as such on the output and identified in the CSR.

All analyses and tabulations will be performed using SAS® software Version 9.4 or higher. Pharmacokinetic and pharmacodynamic (PD) analyses will be performed using Phoenix®

WinNonlin® Version 6.4 or higher. Tables, listings, and figures will be presented in ASCII or RTF format.

The process for SAS program validation and quality control (QC) for programs and outputs is documented in the Synteract working instruction “SAS programming quality control.” Study-specific QC requirements can be found in [Appendix B: SAS Programming QC Requirements](#).

